Population	We will include critically ill children (0 to <18 years of age), admitted to a participating PICU/NICU/CICU, on ECMO, and who have either no bleeding or minimal bleeding within 24 hours of cannulation. We will exclude children with 1) post conception age < 37 weeks at time of screening; 2) underlying oncologic diagnosis or recipient of bone marrow transplant in the last year; 3) congenital bleeding disorder or thrombocytopenia; 4) pregnant or admitted post-partum (within 6 weeks after giving birth); 5) decision to withdraw or withhold some critical care or interventions; and 6) known objection to blood transfusions; or 7) on ECMO for > 24 hours at time of enrollment. Fifty patients will be enrolled in the pilot trial in ten sites (9 in the United States and 1 in Israel). Enrolled means consented and randomized.

Interventions Allocation	Comparator: Higher prophylactic platelet threshold strategy: Patients randomized to this arm will be transfused as soon as the platelet count is $< 90 \times 10^{9}$ cells/L. Intervention: Lower prophylactic platelet threshold strategy: Patients randomized to this arm will be transfused as soon as the platelet count is $< 50 \times 10^{9}$ cells/L. Subjects will be randomized in a 1:1 ratio to either arm. Subjects will be stratified by age (≤ 28 days vs >28 days).
Outcome Measures	 Primary Study Outcome: Pre-transfusion platelet count (supplemented with total volume of platelet transfusions, in mL/kg/day and in mL/kg/run); primary safety outcome: progression to severe bleeding, severe thrombosis, and/or all-cause mortality. Secondary Endpoints: Observed values of estimated separation in mean pre-transfusion platelet counts; eligibility rate relative to predicted rate; enrollment of eligible patients percentage; adjudication rate of progression to severe bleeding/thrombotic outcomes; approach for consent percentage; consent percentage; transfusion compliance rate; transfusion strategy suspension percentage; withdrawal and or lost-tofollow-up percentage; violation of local non-study-specific circulatory support protocol percentage. Tertiary Outcome: A novel composite outcome of severe bleeding and/or severe thrombosis (supplemented with component outcomes of progression to severe bleeding, progression to severe bleeding, progression to severe bleeding, and progression to both severe bleeding and severe thrombosis.

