Subjects will be **stratified by age** (≤28 days vs >28 days) because it is infeasible to stratify by more than one variable given the sample size. We prioritized this variable since most of the safety concerns are around lower transfusion strategies in infants. Other variables considered for stratification in the future large trial will be type of ECMO support (V-A vs V-V) and site.

Patients will not be stratified based on the severity of the disease, as all scores predicting outcome on ECMO use data from the first few days of the ECMO run (43–45). In addition, scores that evaluate severity at admission (PRISM III and PIM2) are not validated nor calibrated in ECMO patients (46,47). In the pilot, we will neither stratify according to the indication (medical vs post-surgical), as this would significantly increase the sample size. However, this may be explored in regression models and sensitivity analyses.

Research personnel at each site and PICU caregivers will not have access to the randomization schedule. Moreover, in order to **conceal randomization**, 3 sizes of **blocks permutation** will be used on a random sequence: 2, 4 and 6 subjects per block.

F. Blinding

This is an open-label trial, since the **transfusion strategy cannot be blinded** from the clinical team, as they must order the transfusions based on the platelet count. The research team ([name], [name], and members of the steering committee) will be blinded to treatment allocation until the end of the analysis. Since the statisticians will need to report to the Data Safety Monitoring Board, they will not be blinded.

G. Treatment Period and Follow Up

The intervention will be implemented immediately upon randomization and maintained in effect until four possible events (whichever occurs first):

- progression to severe bleeding, according to the BASIC definition, and/or severe clotting, according to the NHLBI consensus definition, outside of temporary suspensions
- 2) decannulation from ECMO (or ECMO flow stopped, even if cannulas left in place)
- twenty-one days post-randomization (as the progression to new bleeding and new thrombosis has plateaued by day 21 and 95% of the patients will be off ECMO by then (6))
- 4) or temporary suspension lasting more than 24 hours.
- 5) Withdrawal from the study, either by the attending physician or the parents.

The mortality follow-up will be at 28 (+/- 4 days) and 90 (+/- 10) days after randomization.

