- We will optimize and document the ability to adjudicate a *bleeding and/or thrombotic outcomes* using both the BASIC and NHLBI developed definitions.
- *Eligibility numbers and enrollment rates* will inform the number of centers, size of centers (high volume versus low volume), and location of centers (US-only versus international) required to accrue the required sample size for the subsequent ECSTATIC RCT.
- We will document the ability to enroll patients through standard consent, which will allow us to determine if an Exception From Informed Consent (EFIC) will be needed for the larger RCT. This finding will also contribute to the selection of sites for the larger RCT as some countries have no provision for EFIC.
- *Protocol deviations*, should they occur in the pilot trial, will provide opportunities to refine key protocol elements, including reasons for protocol suspension, in order to maximize protocol adherence and minimize risk of bias in the subsequent ECSTATIC RCT.
- We will document and classify *temporary suspensions* to allow for refinement in the subsequent RCT.

10. Sample Size and Statistical Analysis

A. Sample Size

Salient assumptions to permit power estimation include the number of observed transfusion days per subject, the within-subject dependence structure, the within-treatment variability, and the difference in means between treatments. Previous data, albeit not with an enforced low platelet threshold transfusion strategy, were used to inform the first three assumptions. It was assumed the distribution of the number of transfusion days per subject will mimic historical data (e.g., approximately 10%-20% will have no transfusions). It was assumed a compound symmetry covariance structure will adequately account for within-subject dependence; such a structure is induced by a mixed effects model with subject-specific random intercepts. Fitting a model with such a covariance structure to historical data [6] yielded an estimated autocorrelation slightly above 0.2; to be conservative the power estimation assumed ρ =0.3 (6). The assumed within-treatment standard deviation, 40x10⁹/L, resembles historical data but is anticipated to be a conservative estimate for the trial.

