Although the difference in platelet strategy thresholds is $40x10^{9}/L$ (i.e., $90 \times 10^{9}/L \times 50 \times 10^{9}/L$), this full effect will not be realized for the mean difference because the strategies depend on platelet counts which are not continuously observed, and as such, by the time of measurement a patient may have a platelet count considerably below the threshold. Patients with a platelet count

under 50 x10⁹/L would be transfused under either strategy. Therefore, a more realistic separation for the difference in means between strategies is 30 x10⁹/L.

Assuming pre-transfusion platelet levels will be approximately normally distributed with a difference in means of 30×10^{9} /L, then with **50 patients (25 per arm)** enrolled there would be approximately **81% power** to detect a difference in mean platelet levels at the time of transfusion. Power may be higher due to conservative assumptions.

The design of the *full RCT*, which will test the non-inferiority of a low platelet threshold strategy, will be informed by the separation in pre-transfusion platelet counts in both arms, median number of transfusions in each group, proportion of patients who develop the primary safety outcome (progression to severe bleeding and/or severe thrombotic event and/or study-related death) or tertiary outcome (progression to severe bleeding and/or severe thrombotic event), proportion of patients who require temporary suspension, proportion of patients with non-platelet transfusion protocol violations, and the consent rate.

B. Planned Recruitment Rate

There is a wide heterogeneity in the number of ECMO runs per center and per year. The sum of the eligible patients from the ten centers who have committed to participate in the pilot trial is 79 patients per year. We therefore would require an enrollment rate of 32% to recruit all of the patients within 24 months [50 patients / (2 years x 79 patients per year) = 0.32]. As a result, we are very confident we will complete the pilot trial within 3 years.

All the participating sites have at least 10 ECMO runs per year (the larger sites have up to 50 a year). Therefore, we anticipate that even the smaller sites should be able to enroll 5 patients over 18 months. However, should the enrollment be slower than expected, we will lift the cap on the larger sites (currently set at 10 subjects).

C. Statistical Analysis

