For the *pilot study*, the analysis of the primary outcome measure will be assessing the pretransfusion platelet count to describe the separation between the two platelet transfusion strategies, while accounting for intra-subject correlation. For each arm, we will estimate the mean pre-transfusion platelet count throughout the ECMO runs. This primary outcome will be measured for each transfusion and represent the latest available collected platelet count that is before the transfusion began. In the event that there was no preceding platelet count since a previous transfusion, the outcome for that transfusion will be regarded as missing. Participants who do not have a non-missing value for this outcome (e.g., they had no transfusions) will not be included in the analysis of the primary outcome. Because we anticipate intra-subject correlation when there are multiple transfusions for a patient, we will fit a linear model to pre-transfusion platelet counts with a fixed effect for assigned treatment (higher threshold vs. lower threshold). We will account for repeated measures by considering three within-subject covariance structures with constant variances: compound symmetry; the continuous analog of an autoregressive order 1 process, also known as CAR(1); and a hybrid of compound symmetry and CAR(1) achieved by including random subject effects and CAR(1) correlations in the within-subject errors. We will use restricted maximum likelihood (REML) for model estimation and use the model with the lowest Akaike Information Criterion (AIC) to select the best covariance structure. Once the covariance structure

is determined, the Kenward-Roger calculation for denominator degrees of freedom (df) will be applied in the F-test (equivalently, for the df in the t-test) of the treatment strategy's model coefficient. The test of the null hypothesis that the mean pre-transfusion platelet count is the same for each treatment arm vs the alternative that the higher threshold has a higher mean will be considered statistically significant if and only if the one-sided p-value is less than 0.025. In addition, a two-sided 95% confidence interval for the difference in means will be reported along with estimates of each treatment's mean and the difference in means, with all inferences coming from the repeated measures model described above.

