The first objective is based on the primary outcome of platelet counts before transfusions. Because we anticipate intra-subject correlation when there are multiple transfusions for a participant, we will fit a linear model to pre-transfusion platelet counts with a fixed effect for assigned treatment (Higher threshold, with tmt=1, vs Lower threshold, with tmt=0), such that the outcome's expected value is represented by $\beta_0 + \beta_{tmt}$ for the higher threshold and β_0 for the lower threshold. We will account for repeated measures by considering three covariance structures: compound symmetry (CS), continuous analog of autoregressive order 1, also known as CAR(1), and a hybrid of CS and CAR(1) achieved by including random subject effects and CAR(1) correlations in the within-subject errors. We will use restricted maximum likelihood (REML) for model estimation and use the model with the lowest Akaike Information Criterion (AIC) to select the best covariance structure. Once the covariance structure is determined, the Kenward-Roger calculation for denominator degrees of freedom (df) will be applied in the F-test (equivalently, for the df in the t-test) of the treatment strategy's model coefficient. The one-sided p-value of the null hypothesis $\beta_{tmt} = 0$ vs $\beta_{tmt} > 0$ will be considered statistically significant if and only if this p-value < 0.025. In addition, a two-sided 95% confidence interval for β_{tmt} will be reported. Likewise, estimated means for the lower threshold and the higher threshold arms will be reported as $\hat{\beta}_0$ and $\hat{\beta}_0 + \hat{\beta}_{tmt}$ respectively.

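### The primary separation model omits the age stratum used in randomization; adding it is a nearly free, low-priority improvement that matters only if age relates materially to the pre-transfusion count

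*Combined protocol and SAP*

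**What the plan says.** The protocol abstract fixes the design: "Subjects will be stratified by age (≤ 28 days vs >28 days"). Protocol 8.E explains why age is the only factor, "because it is infeasible to stratify by more than one variable given the sample size", and says age was chosen because of safety concerns about lower thresholds in infants. SAP 3.2 repeats the scheme.

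For the primary analysis, SAP 7.2.1 says "we will fit a linear model to pre-transfusion platelet counts with a fixed effect for assigned treatment". Protocol 10.C has the same model, "with a fixed effect for assigned treatment (higher threshold vs. lower threshold"). Treatment is the only fixed effect, and a within-subject covariance structure handles repeated transfusions. The test "will be considered statistically significant if and only if the one-sided p-value is less than 0.025", and a two-sided 95% interval is reported.

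Age enters only through exploratory subgroup work (Protocol 10.C; SAP 5.4 and 7.6), where a model with age as a covariate is the fallback if subset models are hard to fit. SAP 7.6 says why site is left out of the primary model (risk of non-convergence). It gives no reason for leaving out age. Feasibility criterion SE1 (SAP 2.2.2 and 7.3.1) compares the point estimate from this model with 30 ×10⁹/L.

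**The concern.** When allocation is balanced within age strata, the difference between strata largely cancels out of the treatment contrast. A model without the stratum still counts that difference as between-patient variance, so its standard error overstates the uncertainty. The trial stratifies by age but does not use the resulting balance in its main Aim 1 result.

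A second point concerns the estimate itself. Patients without a usable pre-transfusion count, including those never transfused, leave the primary analysis (Protocol 10.C; SAP 7.2). The analysed set therefore need not keep the age balance created at randomization. Any imbalance moves the unadjusted difference, and SE1 is judged on that difference.

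At stake are the width of the Aim 1 interval and some robustness of the SE1 estimate. The validity of the test is not in question.

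**Working it through.** **Inputs from the documents.**
- Protocol 10.A: "a more realistic separation for the difference in means between strategies is 30" ×10⁹/L.
- Protocol 10.A: within-treatment SD 40, which "is anticipated to be a conservative estimate for the trial".
- Protocol 10.A: historical data "yielded an estimated autocorrelation slightly above 0.2; to be conservative the power estimation assumed" 0.3. Between 10% and 20% of patients are expected to have no transfusion.
- SAP 8: 25 patients per arm, taken as 30 effective independent observations per arm.
- Protocol 6.E: neonates are at least half of children on ECMO.

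**Inputs assumed.** The age gap in mean count (1 to 30); 1.8 or 5 transfusions per transfused patient; an equal age split; 15% untransfused; the same age shift in both arms. The value 1.8 was chosen to match the plan's effective sample size: 25 × 0.85 / (0.3 + 0.7/1.8) = 21.25 / 0.689 ≈ 31 per arm.

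**Step 1: reproduce the stated power.** SE = 40 × √(2/30) = 10.33, and 30/10.33 = 2.905. Normal power is Φ(2.905 − 1.960) = 82.8%. A noncentral t with 58 df gives 81.5%. The plan's figure of about 81% reproduces.

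**Step 2: closed form.** With m transfusions per patient, the variance of a patient mean is SD² × (0.3 + 0.7/m). Leaving out a covariate with an equal split adds gap²/4. The ratio of unadjusted to adjusted SE is the square root of (variance + gap²/4) / variance.
- SD 40, m = 1.8: variance 1102. Gap 10: √(1127/1102) = 1.011. Gap 20: √(1202/1102) = 1.044. Gap 30: √(1327/1102) = 1.097.
- SD 40, m = 5: variance 704. Gap 10: √(729/704) = 1.018. Gap 20: √(804/704) = 1.069. Gap 30: √(929/704) = 1.149.
- SD 30 (assumed), m = 5: variance 396. Gap 10: √(421/396) = 1.031. Gap 20: √(496/396) = 1.119.

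**Step 3: simulation at SD 40.** 50 patients in two strata of 25; 1:1 blocks of 2, 4 and 6; compound symmetry; true difference 30. Each data set was fitted by REML with and without age. Degrees of freedom were analysed patients minus fixed-effect parameters, an approximation to Kenward-Roger. There were 12,000 runs per gap at 1.8 transfusions and 2,000 at 5. Except for the column headed m = 5, results are for 1.8.

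| Age gap | Half-width without / with age | Ratio, m = 1.8 | Ratio, m = 5 | Coverage without / with | Power without / with |
|---|---|---|---|---|---|
| 1 | 21.06 / 21.14 | 0.996 | 0.997 | 94.8% / 94.8% | 79.9% / 79.6% |
| 5 | 21.14 / 21.16 | 0.999 | 1.001 | 94.7% / 94.8% | 79.2% / 79.1% |
| 10 | 21.33 / 21.18 | 1.007 | 1.015 | 95.2% / 95.0% | 79.2% / 79.6% |
| 20 | 22.03 / 21.15 | 1.042 | 1.068 | 95.7% / 94.7% | 76.4% / 78.9% |
| 30 | 23.18 / 21.14 | 1.096 | 1.145 | 96.1% / 94.8% | 72.9% / 79.1% |

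With no age effect the ratios are 0.996 (m = 1.8) and 0.997 (m = 5), so the age term costs 0.3% to 0.4% of width.

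**Step 4: the point estimate.** The unadjusted difference shifts by roughly the gap times the between-arm difference in neonate share among analysed patients. For an assumed 10-point difference in share, that is 0.1 at gap 1, 1 at gap 10 and 2 at gap 20 (×10⁹/L). When untransfused patients drop out at random, as simulated, the gain is small: the SD of the estimate across runs is 10.72 without age and 10.65 with it at gap 20, and 10.82 against 10.59 at gap 30. It could be larger if being untransfused depends on both arm and age, which the simulation did not cover.

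**The case against.** The strongest objection is that the documents' only direct data on this outcome show almost no age gap. In the REDS-IV-P series (Protocol 8.A) the medians for neonates and older children are 72 and 71 for lower-dose transfusions and 113 and 112 for higher-dose ones, with p=0.86 for age. At a gap that small, adjustment gains nothing. The series had no enforced thresholds, so it does not settle what happens in the trial. Protocol 5.A reports falls of 25% to 60% in neonatal counts after cannulation, against about 30% in older children, and faster falls could separate the groups even under a common threshold. That makes an age gap possible; it does not establish one.

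A reader might take the provider survey's medians of 70 for non-bleeding neonates and 50 for non-bleeding children as the expected gap. The same survey gives 75 and 75 for minimal bleeding, and 80 and 75 for resolved bleeding. The gaps are therefore 20, 0 and 5. They are also preferences without an assigned threshold, whereas the trial applies one threshold per arm at every age.

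A reader might also expect much larger gains. An SD of 20 with 4 transfusions per patient gives a variance of 400 × (0.3 + 0.7/4) = 190. The adjusted SE is then 6% smaller at gap 10 (√(190/215) = 0.94) and 19% smaller at gap 20 (√(190/290) = 0.81). But 20 is nowhere in the plan, which uses 40. What stands is that the plan calls 40 conservative, and a smaller true SD would make any given age gap count for more.

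Finally, SE1 does not use the interval and is one of ten criteria of which five suffice. Age subgroup analyses are already planned. These points lower the priority but do not explain the omission.

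**Conclusion.** The age stratum is absent from the primary model and no reason is given. At the plan's SD of 40 and correlation of 0.3, the cost in interval width is nil for age gaps up to about 5 ×10⁹/L, about 1% to 2% at 10, 4% to 7% at 20 and 10% to 15% at 30. It is larger if the true SD is below 40. On the outcome data in the protocol the gap is probably small, so the expected gain is modest. The age term also gives some protection to the SE1 estimate against age imbalance among the patients analysed.

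Three stronger readings are not supported. The interval is not too wide whenever age has any relation to the count, since small gaps give no gain. Type I error is not inflated, because the error is conservative. The stated 81% power is not shown to be lost: the SD of 40 is a within-treatment figure resembling historical data and may already include age variation, in which case 81% describes the unadjusted analysis and adjustment could only add to it.

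The sizes rest on assumed age gaps and transfusion counts, an equal age split, a constant age shift in both arms and approximate degrees of freedom. This is a low-priority improvement and does not change the trial's conclusion.

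**What to change.** In SAP 7.2.1 and Protocol 10.C, add age stratum (≤28 against >28 days) as a fixed effect in the primary model. Report the adjusted treatment difference and interval for Aim 1, use the adjusted difference for SE1, and keep the model without age as a sensitivity analysis. If the sponsor prefers the present model, pre-specify the age-adjusted model as the sensitivity analysis or state why age is omitted.

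The cost is one model term, one degree of freedom and no new data. SAP 1.0 was written against protocol 1.3.1 and the current protocol is 1.4, so the change can go into a SAP update.
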